## 2.2 Trial Diagram

\* ≤ 4 subjects or 33% of Stage 1 subjects does not include infusion reactions (from either study drug) which were subsequently controlled and reduced in Cycle 1 via ameliorating actions, and which did not recur in Cycle 2

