## **3. Dose Reduction**

If a subject experiences an infusion reaction despite having been administered premedication and despite the infusion time being lengthened, the PI may re-challenge the subject at the next visit by dose reducing the Imprime PGG to 2 mg/kg.

All attempts should be made to ameliorate Grade 3/4 infusion reactions by the Investigator following the 3 recommendations provided above sequentially.

In Stage 1, any Grade 3/4 infusion reactions mitigated by these actions and either resolving or decreasing to Grade 1/2, if this mitigation occurs within Cycle 1 and the Grade 3/4 infusion reaction does not recur in Cycle 2, will not be counted towards the total of > 4 or 33% of Grade 3/4 adverse events which require halting the study in Stage 1 for each individual indication. Only Cycle 1 Grade 3/4 infusion reactions (or those which recur in Cycle 2) will be counted towards the total which would halt advancement to Stage 2.

- In the event there are a total of > 4 or 33% of Grade 3/4 adverse events in Stage 1 which were unable to be ameliorated by the sequential recommendations above, the dose of Imprime PGG will be reduced to 2 mg/kg.
- Stage 1 will be repeated with an additional cohort of n=12 subjects at the reduced dose of 2 mg/kg. Toxicity at the dose of 2 mg/kg will be assessed in this additional Stage 1 cohort in the same manner as was done for the initial dose of 4 mg/kg, with the identical sequential recommendations for any observed infusion reactions.
- Advancement to Stage 2 will be halted if there are > 4 or 33% of Grade 3/4 adverse reactions. Otherwise, subjects will proceed to Stage 2 with all subjects at the new, reduced dose of 2 mg/kg.

Note that continuation onto Stage 2 requires a demonstration of at least 1 or 2 objective responses in subjects with melanoma or TNBC, respectively, in addition to meeting the adverse event requirements detailed above, at either Imprime PGG dose of 4 mg/kg or 2 mg/kg. Please refer to the [Trial Diagram](#) in [Section 2.2](#) for a schema of the study flow from start to end.

In general, any Grade 4 non-infusion or non-hematological AE will lead to the withdrawal of the subject from treatment. A dosing delay of up to 3 weeks is allowed in case of Grade 3 non-hematological AEs to reduce toxicity to baseline or Grade 0-1. Dose levels will be adjusted individually for each study drug.

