Grades 3 or 4  Grade 3: Prolonged (ie, not rapidly responsive to symptomatic medication and/or brief interruption of infusion); recurrence of symptoms following initial improvement; hospitalization indicated for other clinical sequelae (eg, renal impairment, pulmonary infiltrates)  Grade 4: Life-threatening; pressor or ventilatory support indicated	
Stop Infusion.            Additional appropriate medical therapy may include but is not limited to:
 
 
Epinephrines**
 
IV fluids
 
Antihistamines
 
NSAIDS
 
Acetaminophen
 
Narcotics
 
Oxygen
 
Pressors
 
Corticosteroids
 
 
Increase monitoring of vital signs as medically indicated until the subject is deemed medically stable in the opinion of the Investigator.            Hospitalization may be indicated.            **In cases of anaphylaxis, epinephrine should be used immediately.  Subject is permanently discontinued from further study drug treatment.
	No subsequent dosing

Appropriate resuscitation equipment should be available at the bedside and a physician readily available during the period of drug administration.

For further information, refer to the Common Terminology Criteria for Adverse Events v4.03 (CTCAE) at <http://ctep.cancer.gov>

In Stage 1, any Grade 3/4 infusion reactions mitigated by these actions and either resolving or decreasing to Grade 1/2, if this mitigation occurs within Cycle 1 and the Grade 3/4 infusion reaction does not recur in Cycle 2, will not be counted towards the total of > 4 or 33% of Grade 3/4 adverse events which require halting the study in Stage 1 for each individual indication. Only Cycle 1 Grade 3/4 infusion reactions not controlled by the above measures (or those which recur in Cycle 2) will be counted towards the total which would halt advancement to Stage 2.

Dose will be managed individually for each study drug.

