### **9.1.3 Efficacy Analyses**

Efficacy analysis will be conducted separately for each tumor type. The primary efficacy endpoint is ORR, and the secondary efficacy endpoints include PFS, TTR, CRR, DoR and OS. The primary efficacy population will include all evaluable subjects who receive at least one dose of study treatment, have measurable disease at baseline per RECIST v1.1, and have at least one post-baseline scan or discontinue study treatment as a result of progressive disease, death, or a treatment-related adverse event before the first post-baseline scan.

Hypotheses testing of ORR will be conducted among evaluable subjects at the dose which meets the safety criterion in Stage 1. Among the 12 evaluable subjects in Stage 1, at least 1 objective response in melanoma subjects would be needed to proceed to Stage 2 for melanoma; and at least 1 objective response in TNBC subjects would be needed to proceed to Stage 2 for TNBC. If there are at least 4 objective responses among the total of 29 evaluable subjects with melanoma and/or at least 5 objective responses among the total of 41 evaluable subjects with TNBC, the null hypothesis will be rejected for melanoma and/or TNBC and the study will be declared a success.

The point estimate along with the exact 95% confidence interval will be computed for ORR and CRR. PFS and OS will be summarized descriptively and graphically using the Kaplan-Meier method. The Kaplan-Meier estimate for the median, first, and third quartiles will be determined along with 95% confidence intervals (CIs). The Brookmeyer-Crowley method will be used for the CI calculations. For the subset of subjects who have a CR or PR, TTR and DoR will be summarized similarly using the Kaplan-Meier method. The Kaplan-Meier

estimate of PFS rate at the landmark times of 6 months and 1 year, and the OS rates at the landmark time of 1 year will be calculated.

Exploratory analyses may be conducted using iRECIST.

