4 STUDY DESIGN

This is a Phase 2 study of Imprime PGG and pembrolizumab in subjects with advanced melanoma failing front-line treatment with checkpoint inhibitors or TNBC failing front-line chemotherapy for metastatic disease.

The study design is based on hypothesis testing of the ORR for pembrolizumab + Imprime PGG. For melanoma subjects, the null hypothesis is $ORR \leq 5\%$, versus the alternative hypothesis of $ORR \geq 23\%$; for the TNBC subjects, the null hypothesis is $ORR \leq 5\%$ ($ORR=5\%$ in KEYNOTE-086), and the alternative hypothesis is $ORR \geq 21\%$. Hypotheses testing will be conducted using a one-sided type I error of 0.05.

The study will incorporate Simon's optimal 2-stage design with sample size fixed at 12 subjects each in Stage 1 for advanced melanoma and for TNBC subjects. The safety criterion of ≤ 4 (or $\leq 33\%$) subjects with Grade 3/4 adverse events in Cycle 1 within either tumor type must be met in order to proceed to Stage 2 (Grade 3/4 infusion reactions which occur during Cycle 1 that either resolve or decrease to Grade 1/2 and recur in Cycle 2, will not be counted towards the total of ≥ 4). The starting dose is 4 mg/kg for Imprime PGG. In the event there are a total of > 4 (or $> 33\%$) of subjects with Grade 3/4 adverse events in Cycle 1, the dose of Imprime PGG will be reduced to 2 mg/kg, and Stage 1 will be repeated at a dose of 2 mg/kg with an additional cohort of $n=12$ subjects. For the dose that meets the safety criterion in Stage 1, at least 1 response in melanoma subjects and 1 response in TNBC subjects amongst the 12 subjects within each tumor type must be observed in order to proceed to Stage 2. Stage 2 will enroll an additional 17 subjects with melanoma, and 29 subjects with TNBC. For the dose that meets the Stage 1 safety criterion, success will be declared if at least 4 amongst the total of up to 29 subjects with melanoma, and 5 amongst the total of up to 41 subjects with TNBC achieve an objective response. The above design corresponds to a type I error 0.05 and power of 90% for both melanoma and TNBC.

The dosing schedule and the study assessments are presented in the schedule of assessment in the protocol.

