5 PLANNED ANALYSES

5.1 Interim Analyses

An informal interim analysis was conducted at the end of Stage 1 to assess the safety criterion for each tumor type and confirm the dose of Imprime PGG before continuing enrollment in Stage 2. Overall response rate based on RECIST 1.1 and adverse events including Grade 3/4 adverse events were considered for decision-making. Safety data will be summarized periodically throughout the study as part of ongoing safety review.

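### SAP section 4 reverses the Protocol's infusion-reaction exemption in the Stage 1 safety gate: it leaves out controlled reactions that recur in Cycle 2, where the Protocol leaves out only those that do not

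*SAP*

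**What the plan says.** Both documents set the same gate for each tumour type. In a Stage 1 cohort of 12, at most 4 subjects (33%) may have a counted Grade 3/4 adverse event in Cycle 1. With more than 4, Imprime PGG falls from 4 to 2 mg/kg and Stage 1 is repeated in 12 further subjects. The documents differ on which infusion reactions count.

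- Protocol 2.2 (note to the trial diagram) leaves out reactions "which were subsequently controlled and reduced in Cycle 1 via ameliorating actions, and which did not recur in Cycle 2".
- Protocol 5.2.1.2.1 (Imprime PGG, dose reduction) leaves out a mitigated Grade 3/4 reaction "if this mitigation occurs within Cycle 1 and the Grade 3/4 infusion reaction does not recur in Cycle 2, will not be counted".
- Protocol 5.2.1.2.2 (text below Table 2) has the same exemption and adds the converse: "Only Cycle 1 Grade 3/4 infusion reactions not controlled by the above measures (or those which recur in Cycle 2) will be counted".
- SAP 4 describes the exempt infusion reactions of this severity as those "which occur during Cycle 1 that either resolve or decrease to Grade 1/2 and recur in Cycle 2, will not be counted".

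The gate fixes the dose on which efficacy is judged. Protocol 9.1.3: "Hypotheses testing of ORR will be conducted among evaluable subjects at the dose which meets the safety criterion in Stage 1". SAP 5.1 records that the gate has already been applied: "An informal interim analysis was conducted at the end of Stage 1 to assess the safety criterion for each tumor type".

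**The concern.** Taken literally, the SAP exempts the clinically worse event, a severe reaction that comes back after it was controlled. By implication it counts the milder one, a severe reaction that was controlled and stayed away. The error can therefore act in either direction. It can let through a dose that the Protocol would reduce, or reduce a dose that the Protocol would keep. The SAP wording also omits the Protocol's condition that control be achieved within Cycle 1.

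At stake is the written basis of the dose decision. Safety of the combination is part of the primary objective, and the SAP neither flags nor explains a change of rule.

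**Working it through.** **The texts side by side** (a Cycle 1 Grade 3/4 infusion reaction that is controlled within Cycle 1)

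| Course in Cycle 2 | Protocol | SAP 4, read literally |
|---|---|---|
| Does not recur | not counted | counted (by implication) |
| Recurs | counted | not counted |

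One sentence in Protocol 5.2.1.2.1 says loosely that Cycle 1 infusion reactions are counted, without mentioning control. The sentence before it gives the exemption in full, and the bullet after it limits the trigger to events "which were unable to be ameliorated by the sequential recommendations above". The Protocol's meaning is not in doubt.

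**The plan's own figures.** 4/12 = 33.3% passes and 5/12 = 41.7% fails, which agrees with the stated 33% limit. The SAP parenthesis gives the total as ≥ 4, but the gate is stated correctly just before it (≤ 4) and just after it (> 4). That slip is editorial.

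**When the verdicts differ.** Place each of the 12 subjects in at most one group:

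- A: has another counted Grade 3/4 event.
- N: has only a controlled reaction that did not recur.
- R: has only a controlled reaction that recurred.

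The Protocol counts A + R and the SAP counts A + N. Each passes the dose if its count is 4 or fewer.

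- A = 4, R = 1, N = 0: Protocol 5 (fail), SAP 4 (pass).
- A = 4, N = 1, R = 0: Protocol 4 (pass), SAP 5 (fail).

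There are 455 combinations with A + N + R ≤ 12, and 200 of them give opposite verdicts. All 200 have A ≤ 4 and A + N + R ≥ 5. No rate has to be assumed for this result.

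**How often, under assumed rates.** The documents give no rates. Let a be the rate of other counted events (10% to 35%), c the rate of subjects with only a controlled reaction (2% or 5%), and q the share of those that recur (0% to 50%). The counts are multinomial with n = 12 and probabilities a for A, c(1 − q) for N and cq for R.

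- Unsafe direction (Protocol fails, SAP passes): P(A + R ≥ 5 and A + N ≤ 4).
- Opposite direction (Protocol passes, SAP fails): P(A + R ≤ 4 and A + N ≥ 5).

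At q = 0 there is no R, so the unsafe direction is exactly 0. The opposite direction is P(Bin(12, a) ≤ 4) − P(Bin(12, a + c) ≤ 4). For a = 35%:

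- c = 2%: 0.5833 − 0.5249 ≈ 0.0585
- c = 5%: 0.5833 − 0.4382 ≈ 0.1452

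At q = 50%, N and R have equal rates, so each direction is half of the total. For a = 35%:

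- c = 2%: 5.27%/2 ≈ 2.63%
- c = 5%: 11.45%/2 ≈ 5.73%

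Probability (%) per cohort of 12, by rate of other events:

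| c | q | Direction | 10% | 15% | 20% | 25% | 30% | 35% |
|---|---|---|---|---|---|---|---|---|
| 2% | 0% | unsafe | 0 | 0 | 0 | 0 | 0 | 0 |
| 2% | 0% | opposite | 0.52 | 1.53 | 2.96 | 4.40 | 5.44 | 5.85 |
| 2% | 50% | each | 0.21 | 0.65 | 1.30 | 1.95 | 2.44 | 2.63 |
| 5% | 0% | unsafe | 0 | 0 | 0 | 0 | 0 | 0 |
| 5% | 0% | opposite | 1.96 | 4.86 | 8.51 | 11.87 | 14.03 | 14.52 |
| 5% | 50% | each | 0.61 | 1.72 | 3.18 | 4.57 | 5.49 | 5.73 |

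**Check on the ORR design.** The chance of rejecting the null is the sum over x = 1 to 12 of P(Bin(12, p) = x) · P(Bin(n₂, p) ≥ r − x), with n₂ = 17, r = 4 for melanoma and n₂ = 29, r = 5 for TNBC.

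- Early termination under the null: 0.95¹² = 0.540 (stated 0.54).
- Melanoma: alpha 0.0500, power 0.902.
- TNBC: alpha 0.0452, power 0.906.

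These agree with the stated 0.05 and 90%. The infusion-reaction count does not enter the formula.

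**The case against.** The best defence is that the sentence does no work. It is a parenthesis in a recap of the design. SAP 1 sends the reader to Protocol version 2.0 for the design, and the Protocol states the rule correctly in three places. The review was finished when the SAP was written, and no analysis in the SAP text available uses the parenthesis. Much of this stands, and it limits the consequence. It does not make the sentence right. A signed analysis plan states a dose-decision rule with the opposite sign and flags no change, and SAP 5.1 does not say which rule the review applied.

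A reader might go further and infer that the gate count must now be rebuilt from listings, because SAP 12.2 groups adverse events by periods of months and not by Cycle 1. The documents do not support that. Protocol 9.1.6 plans a summary of events of Grade 3 or higher at the interim analysis, and SAP 5.1 says that Grade 3/4 events were considered there. The display lists that SAP 10 and 11 refer to are not in the text available, so a Stage 1 display cannot be ruled out.

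A reader might also add the two directions and quote the peaks of 5.85% and 14.52% as the chance of an unsafe dose. Those peaks occur at zero recurrence, where every disagreement has the SAP as the stricter rule.

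**Conclusion.** The concern holds as a reversed rule in the SAP that should be corrected. The reversal itself is certain from the text, and a dropped *do not* is the likely cause. One subject can change the verdict when four others already count.

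For other events of 10% to 35% and recurrence of 0% to 50%, the unsafe direction has a probability of 0% to 2.63% per cohort if 2% of subjects have only a controlled reaction, and 0% to 5.73% if 5% do. The opposite direction is 0.21% to 5.85% and 0.61% to 14.52%. These figures rest on assumed rates, on every controlled reaction being controlled within Cycle 1, and on the SAP sentence being applied literally. The largest values fall at 35% other events, where the gate is close to a coin toss even under the correct rule (Protocol pass probability 51% to 58%).

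It would be wrong to infer that the dose was chosen under the reversed rule, since nothing in the documents shows this. It would also be wrong to infer that the ORR test is compromised, since its alpha and power are unaffected.

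**What to change.** 1. Replace the parenthesis in SAP 4 with wording to this effect: *Cycle 1 Grade 3/4 infusion reactions that resolve or fall to Grade 1/2 within Cycle 1, and do not recur in Cycle 2, are left out of the count towards the total of > 4.* This restores the negation and the Cycle 1 limit, and it corrects the ≥ 4.
2. State in the study report which counting rule the completed Stage 1 review used. If it was not the Protocol rule, state for each tumour type whether the verdict is the same under the Protocol rule.

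The cost is one SAP sentence and one or two sentences in the report. A recount is needed only if the review departed from the Protocol rule, and it covers 12 subjects per cohort. It can stop early if fewer than 5 subjects had any Cycle 1 Grade 3/4 event, or if more than 4 had one that was not an infusion reaction, because both rules then agree. The Protocol needs no change for this point.

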5 PLANNED ANALYSES

5.1 Interim Analyses

An informal interim analysis was conducted at the end of Stage 1 to assess the safety criterion for each tumor type and confirm the dose of Imprime PGG before continuing enrollment in Stage 2. Overall response rate based on RECIST 1.1 and adverse events including Grade 3/4 adverse events were considered for decision-making. Safety data will be summarized periodically throughout the study as part of ongoing safety review.

5.2 Primary Analyses

The primary analyses for the melanoma and TNBC subjects will be conducted when all subjects have completed the treatment phase of the study. All data will be included in the primary analyses and each tumor type will be analyzed separately.

5.3 Final Analysis

The final analysis will be conducted after study completion. Study completion is defined as the death of at least 70% of subjects or 3 years after the last subject's first dose, whichever occurs earlier. Overall survival data will be included in the final analysis.

6 ANALYSIS POPULATIONS

The **ABA pre-screening** population will comprise all subjects who have been pre-screened for ABA test only (who have signed the ABA informed consent form but not the full informed consent form).

The **Screening** population will comprise all subjects who have been screened for the study (who have signed the full informed consent form).

The **All Treated** population will comprise all subjects in the Screening population who receive at least one dose of study treatment. The All Treated population will be the primary population for the baseline characteristics and safety analysis and the secondary population for the efficacy analysis.

The **Evaluable** population will comprise all subjects in the All Treated population who 1) have measurable disease at baseline per RECIST 1.1, AND 2) have at least one post-baseline radiological disease assessment, or discontinue study treatment as a result of progressive disease, death, or a treatment-related adverse event before the first post-baseline radiological disease assessment. The Evaluable population will be the primary population for the efficacy analysis.

The **Per-Protocol** population will comprise all subjects in the All Treated population who do not have any important protocol deviations (IPD) as defined in the study IPD list. The Per- Protocol population will be the tertiary population for the efficacy analysis.

In the Screening population, subjects who do not meet eligibility criteria will be defined as screen failures, and subjects who meet all eligibility criteria but do not receive any study treatment will be defined as non-treated subjects. The Screening population will comprise of All Treated subjects, non-treated subjects, and screen failure subjects.

Limited data will be collected for the ABA pre-screening population and the non-treated subjects and screen failure subjects in the Screening population. Summaries of these data may be produced:

- ABA Pre-screening population: ABA level at screening, demography, inclusion/exclusion, adverse event (if any), concomitant medication (if any) and death data will be collected;
- Screen failure subjects: ABA level at screening, demography, inclusion/exclusion, adverse event (if any), concomitant medication (if any) and death data will be collected;
- Non-treated subjects: ABA level at screening, all other data that are planned to be collected at screening for All Treated subjects, adverse event (if any), concomitant medication (if any), death (if any) and end of study record will be collected.

7 TREATMENT COMPARISONS

As this is a single arm study for each tumor type, the primary endpoint ORR is compared against the historical control ORR as defined in the null hypothesis. The primary objective will be achieved through a test of the hypotheses evaluating ORR in the Evaluable population using a one-sided alpha level of 0.05.

8 GENERAL CONSIDERATIONS FOR DATA ANALYSES

Clinical Data Interchange Standard Consortium (CDISC) Study Data Tabulation Model (SDTM) and Analysis Data Model (ADaM) will be used for the primary and final data analyses.

Data analysis will be conducted separately for the melanoma and the TNBC tumor types.

Summary tables/figures will be provided separately for the melanoma and the TNBC tumor type, and all summary tables will be produced by dose level (if there are >1 dose levels for a tumor type). Listings will be provided with both tumor types being included in one listing, and all listings will be sorted by cancer type (melanoma then TNBC), site ID, subject ID, and then by visit date and time.

All analyses will be performed using SAS® Version 9.4 or higher. Continuous variables will be summarized with number of subjects (n), mean, median, standard deviation, minimum and maximum, and categorical variables will be summarized with frequency counts and percentages.

In the event that the study is prematurely discontinued, all available data will be listed and a review will be carried out by the study team to assess which statistical analyses are still considered appropriate.

Deviations from the planned analyses in the SAP will be identified in the study report.

8.1 Multicenter Study

It is anticipated that subject accrual will be spread thinly across sites and summaries of data by site would be unlikely to be informative, therefore the data from all participating sites will be pooled prior to the analysis.

8.2 Examination of Subgroups

The following subgroups may be explored in the efficacy analysis for the melanoma subjects if the subgroups are large enough to result in meaningful analyses:

- IgG anti-β-glucan antibody (higher vs lower at baseline)
- Previous anti-CTLA-4 inhibitor (ipilimumab) treatment (Yes vs No)
- PD-L1 expression (if sample analyses are run)
- Number of prior systemic regimens for metastatic disease
- ECOG performance (0 vs 1)
- BRAF V600 mutation
- Prior BRAF or MEK inhibitor
- LDH level (normal vs elevated at baseline)
- Liver metastasis (Yes vs No at baseline)

The following subgroups may be explored in the efficacy analysis for the TNBC subjects if the subgroups are large enough to result in meaningful analyses:

- IgG anti-β-glucan antibody (higher vs lower at baseline)
- PD-L1 expression (if sample analyses are run)
- Number of prior systemic regimens for metastatic disease
- Prior hormone therapy (Yes vs No; number of regimens)
- ECOG performance status (0 vs 1)
- LDH level (Normal vs elevated at baseline)
- Liver metastasis (Yes vs No at baseline)

Additional subgroups may be explored for efficacy data analysis if needed.

